8.2 Visit 1 (3 months)

This will be performed three months after commencing the supplement or placebo (with a window of 2 weeks on either side). Blood samples for biochemistry and specialised biochemistry will be repeated. Stool samples will be collected for microbiome analysis. The presence and severity of bone pain localised to sites affected by PDB will be recorded. Health related quality of life assessed by SF36 will be recorded. Any adverse events that have occurred since the baseline visit will be recorded. Capsule and tablet counts will be performed to assess adherence. Participants will be given a second 3-month supply of the intervention they have been allocated to at this visit.

8.3 End of study visit (6 months)

The end of the study visit will be performed six months after commencing the supplement or placebo (with a window of 2 weeks on either side). Blood samples for biochemistry and specialised biochemistry will be repeated. The presence and severity of bone pain localised to sites affected by PDB will be recorded. Health related quality of life assessed by SF36 will be recorded. Stool samples will be collected for microbiome analysis. Any adverse events that have occurred since the last visit will be recorded. Capsule and tablet counts will be performed to assess adherence. The schedule of study assessments is summarised in Table 1.

Table 1. Schedule of study assessments

	Baseline	3 months	6 months
Medical history	X		
Current and recent drug treatments	X	X	X
Adverse events		X	X
Blood for routine biochemistry	X	X	X
Blood for routine haematology	X		
Blood for specialised biochemistry	X	X	X
Stool sample	X	X	X
SF36	X	X	X

Pain at affected site	X	X	X
Blood for genetic analysis	X		
Blood for transcriptome analysis	X		

9. Processing and analysis of samples

All samples will be labelled with a Study ID barcode. These will be supplied to sites ahead of participant recruitment. Details of the labelling system can be found in Section 11.1.

9.1 Routine biochemistry and haematology

The samples for routine biochemistry and haematology will be analysed at the local hospital laboratories for calcium, albumin, LFT, and serum creatinine and 25(OH) vitamin D.

9.2 Specialised biochemistry

These samples will be analysed centrally. A venous blood sample of up to 10ml will be collected into a plain tube and allowed to clot. Serum will be separated on site and 1ml aliquots prepared. The separated serum samples may be stored at -20°C on a short-term basis for up to 48hr before transfer to a low temperature (-70°C or below) freezer for longer term storage until the sample is sent to the central laboratory. These samples will be shipped on dry ice to the co-ordinating centre at the University of Edinburgh Bone Research Laboratory or to the University of East Anglia where the biochemical analyses will be performed in collaboration with [name] and [name] [name].

9.3 Samples for Genetic and Epigenetic Analysis

Samples of up to 10ml will be collected into a potassium EDTA tube at study centres and sent in an approved container system by post to the co-ordinating centre. Alternatively, the EDTA samples may be stored at -20°C on a short-term basis for up to 48hr before being frozen at -70°C or below until they are shipped to the co-ordinating centre on dry ice for DNA extraction and analysis

Any unused samples will be stored for up to 15 years at the co-ordinating centre for ethically approved research projects of relevance to PDB. Consent will be sought for long-term storage of samples and explicitly for genetic analysis.

9.4 Samples for transcriptome analysis

A venous blood sample of up to 3.5ml will be collected into a PaxGene tube (or similar) for transcriptome analysis.

9.5 Samples for microbiome analysis

Stool samples will be obtained for characterisation of the intestinal microbiome. Participants will be given a container and packaging with instructions on how to collect the stool samples at home. Samples will be posted back to the study centre or sent directly to coordinating centre.

10. DATA COLLECTION AND STORAGE

Data will be entered directly onto an electronic case record form (eCRF) by research staff at the study centres. For convenience, printed copies of the CRF will be provided to study centres so that the local research teams can complete the forms prior to entering onto the CRF. Following entry to the eCRF, the data will be stored on a REDCap database held on servers at the Institute of Genetics and Cancer at the University of Edinburgh. REDCap data backups are stored locally but also a secondary copy is securely sent to an encrypted container on DataStore. Access to the database will be username and password protected and limited only to staff members integral to the study. Anonymised data will be downloaded to password protected computers for statistical analysis.

11. DATA MANAGEMENT

11.1 Personal data

No personal identifiable data that will be held on the study database. The participant's normal NHS healthcare provider will hold personal data in a recruitment log held locally for administrative purposes. **Participants will be pseudonymised using a unique study number ([PriP][Centre ID][Participant ID] i.e. PRiP001001). Linkage databases to match participants with their Study IDs for the purposes of re-contacting and accessing medical records will be held at each site and will not be accessible by the central research team.**

11.2 Transfer of Data

Data which would allow the participant to be identified (including personal data) will not be transferred to individuals or organisations outside of the NHS organisation(s) recruiting the participants.

11.3 Data controller

The University of Edinburgh and NHS Lothian are joint data controllers along with any other entities involved in delivering the study that may be a data controller in accordance with applicable laws in force at the time.

11.4 Data Breaches

Any data breaches will be reported to the University of Edinburgh and NHS Lothian Data Protection Officers who will onward report to the relevant authority according to the appropriate timelines if required.

12. STATISTICS AND DATA ANALYSIS

12.1 Sample size calculation

A sample size of 75 participants has been chosen to provide 25 subjects in each treatment group. The hypothesis to be tested is that we will observe a reduction of at least 0.6 of a standard deviation difference in PINP in the calcium and vitamin D group or the probiotics group as compared with the placebo group at 6 months where we expect no change to occur. According to this assumption, the sample size of 25 subjects per group will provide 82% power to detect such a change.

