6. STUDY POPULATION

6.1 Number of participants

A total of 75 patients with PDB will be studied to give 25 patients in each treatment group

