7.3 Withdrawal of participants

Subjects will be informed that they have the right to withdraw from the study at any stage without having to give a reason. They will be advised that if they do withdraw it will not impact on the normal medical care they receive. If the participant does decide to withdraw from the study, two options will be given

- Complete withdrawal: No further contact from the study team and destruction of all data gathered and all samples collected up until the point of withdrawal.
- Partial withdrawal: Termination of study procedures up to the time of withdrawal with retention of samples and data up to that point. Participant consents to being contacted by study team about future studies that may be of interest.

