12.2 Proposed analyses

Analysis of the primary endpoint will be to evaluate changes in PINP in each treatment group between baseline and the study endpoint using by analysis of covariance (ANCOVA) to take account of baseline differences between groups.

Analysis of the secondary endpoints will similarly employ ANCOVA to evaluate differences between the treatment groups.

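### The 82% power in section 12.1 assumes that none of the 25 participants per group lacks a 6-month PINP, because the number recruited is also the number powered on

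*Protocol*

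**What the plan says.** Protocol section 6.1 sets the size of the trial: "A total of 75 patients with PDB will be studied to give 25 patients in each treatment group". Section 12.1 repeats it, "A sample size of 75 participants has been chosen to provide 25 subjects in each treatment group", and attaches the power to that same number: "the sample size of 25 subjects per group will provide 82% power to detect such a change". The effect is "a reduction of at least 0.6 of a standard deviation difference in PINP" in either active group, "as compared with the placebo group at 6 months where we expect no change to occur". Alpha, sidedness, the test, the type of standard deviation and an expected loss are not given.

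Section 7.3 allows withdrawal at any stage, without a reason, in two forms. One is "Complete withdrawal: No further contact from the study team and destruction of all data gathered and all samples collected up until the point of withdrawal". The other, partial withdrawal, stops study procedures but keeps the samples and data already obtained. Section 5.1 places the primary endpoint at six months. Section 12.2 plans to "evaluate changes in PINP in each treatment group between baseline and the study endpoint" by ANCOVA. No section provides for replacing participants who withdraw.

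**The concern.** A power figure applies to the number of participants who supply the outcome. Here that number equals the number recruited, so 82% describes a trial in which all 75 people supply a PINP value after six months of daily product and three visits. The protocol foresees withdrawal, and both of its forms mean that someone who leaves early has no 6-month value. After complete withdrawal no baseline value remains either.

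The interpretation of the result is at stake. If the trial shows no difference, readers will judge that finding against 82%. With any loss, the power of whichever test the figure belongs to is lower than at 25 per group, and nothing in the protocol tells them by how much.

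**Working it through.** **Inputs from the protocol:** 25 per group (6.1, 12.1), difference 0.6 SD (12.1), stated power 82% (12.1), ANCOVA on baseline (12.2).

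**Assumptions, because the protocol is silent:** two-sided alpha 0.05, and loss of 8%, 12% or 20%, which leaves 25 × 0.92 = 23, 25 × 0.88 = 22 or 25 × 0.80 = 20 per group. Loss is taken as equal across groups.

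**Step 1: reproduce 82%.** The noncentral t distribution is used throughout.

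- One-sample (within-group) t test: df = n − 1, noncentrality = 0.6 × √n. At n = 25, noncentrality = 0.6 × 5 = 3.00, critical value t(24) = 2.064, power 82.1%. This matches.
- Two-group t test, active against placebo: df = 2n − 2, noncentrality = 0.6 × √(n/2). At n = 25, noncentrality = 2.121, critical value t(48) = 2.011, power 54.7%. This does not match.
- ANCOVA, active against placebo: the 0.6 is read as a multiple of the SD of PINP between people, so the effect becomes 0.6/√(1 − r²), with df = 2n − 3. At r = 0.69 the effect is 0.829 and the power at n = 25 is 81.9%. This matches, but only with a correlation that the protocol does not state.

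A further route gives 82.4% by simulation: at least one active group significant at one-sided 5%, unadjusted, with both truly effective. It also needs inputs that are not stated, and it is not carried further here.

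**Step 2: repeat with fewer analysed per group.**

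| Basis | 25 | 23 (8% loss) | 22 (12%) | 20 (20%) |
|---|---|---|---|---|
| One-sample | 82.1% | 78.5% | 76.5% | 72.1% |
| Two-group, unadjusted | 54.7% | 51.2% | 49.4% | 45.6% |
| ANCOVA, r = 0.5 | 67.0% | 63.2% | 61.2% | 56.9% |
| ANCOVA, r = 0.69 | 81.9% | 78.5% | 76.6% | 72.3% |
| ANCOVA, r = 0.75 | 88.1% | 85.2% | 83.6% | 79.8% |

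**Step 3: size of the fall.** On the two bases that return 82% (one-sample, and ANCOVA with r = 0.69), 8% loss costs 3 to 4 points, 12% costs 5 to 6 and 20% costs about 10. For the unadjusted comparison with placebo, the cost is 54.7 − 51.2 = 3.5 points at 8% and 54.7 − 45.6 = 9.1 points at 20%. A single loss per group is minor: the one-sample figure at n = 24 is 80.4%.

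**Step 4: loss against the choice of basis.** With no loss at all, the figure at 25 per group ranges from 54.7% (no covariate gain) to 88.1% (r = 0.75). That range is wider than the effect of any loss considered here, so a restatement of power has to fix the test and the correlation as well as the number analysed.

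**The case against.** The sentence in 12.1 is conditional: 25 per group give 82%. Losses do not make it false, and on a one-sample basis it reproduces. Section 6.1 does not use the words enrolled, randomised or analysed, so 25 could be meant as completers. A participant who withdraws partially after the 3-month visit leaves usable samples, and how such data are used is commonly settled in a statistical analysis plan, which is not at hand.

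Part of this stands. No slip of arithmetic is shown, and reading 25 as the number recruited is an inference. It is the natural one, since 75 is the only total given and no replacement or over-recruitment is described. An analysis plan can decide how to use a 3-month value, but it cannot recover data destroyed on complete withdrawal. The number recruited and the power claimed for it are fixed in the protocol.

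Four stronger readings are tempting, and the documents do not support them:

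- A reader might infer that the trial is certain to miss 82%. The protocol gives no loss rate, so the shortfall rests on an assumed one.
- A reader might take 82% as a ceiling. Under ANCOVA it is not: with r = 0.75 power is 88.1% at 25 per group and still 83.6% at 22.
- A reader might infer that every withdrawal erases data. Section 7.3 attaches destruction to complete withdrawal only. The power figures above do not depend on that rule; what counts is the missing 6-month value.
- A reader might think that a loss allowance alone would make 82% right. It would not: the hypothesis in 12.1 is a comparison with placebo, and 25 analysed per group give 54.7% for that comparison without covariate gain.

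**Conclusion.** The point holds in a limited form. Sections 6.1 and 12.1 use 25 per group for two different quantities, and the stated power is tied to complete 6-month PINP data, although section 7.3 provides for withdrawal. At an assumed 8% to 20% loss the cost is roughly 3 to 10 points on either basis that returns 82%, and 3.5 to 9 points for an unadjusted comparison with placebo. These sizes rest on a two-sided alpha of 0.05, a 0.6 SD effect and equal loss across groups. The absolute level under the planned ANCOVA cannot be given from the protocol, because it depends on the correlation between baseline and 6-month PINP. Loss is the smaller of the two uncertainties; both belong in one restated calculation.

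**What to change.** Keep 75 randomised; no extra recruitment is needed. In section 6.1, say that 25 per group is the number randomised. In section 12.1, state the expected number per group with a 6-month PINP and the loss assumed to reach it. Then restate the power, or the detectable difference, at that number for the between-group ANCOVA against placebo, giving alpha and the assumed baseline correlation. The restatement should not use the one-sample basis, which at 20 to 23 per group would print about 72% to 79% for a test that is not the comparison with placebo.

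The cost is a few sentences in two sections at the next amendment. Design, endpoint and planned analysis stay as they are. The downside is that the stated power will probably be less favourable.

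### The 82% power in section 12.1 does not follow from its stated inputs: an unadjusted 25 v 25 comparison at 0.6 SD has about 55%, and the gain from ANCOVA rests on a correlation not given

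*Protocol*

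**What the plan says.** Section 12.1 of the protocol fixes the size of the trial: "A sample size of 75 participants has been chosen to provide 25 subjects in each treatment group". Section 6.1 repeats the same total and split. The effect is "a reduction of at least 0.6 of a standard deviation difference in PINP", and the comparison is "in the calcium and vitamin D group or the probiotics group as compared with the placebo group at 6 months". Placebo is described as the group "where we expect no change to occur". The conclusion drawn is that "the sample size of 25 subjects per group will provide 82% power to detect such a change".

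Section 12.1 gives no alpha, no sidedness, no allowance for loss, no baseline to 6-month correlation, and no statement of which standard deviation the 0.6 is measured in. Section 12.2 plans ANCOVA on baseline for the primary endpoint, but section 12.1 does not mention covariate adjustment.

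**The concern.** The hypothesis is a difference between two randomised groups of 25, so its standard error has to carry the sampling variation of both means. At 0.6 SD, 25 per group is well short of what a two-sample test needs for power above 80%. This calculation is the protocol's only justification for 75 participants, and it concerns the primary endpoint. If the figure belongs to a different test from the one hypothesised, anyone using section 12.1 to judge what the trial can detect is working from an unsupported number.

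**Working it through.** **Inputs.** From sections 6.1 and 12.1: n = 25 per group, three groups, d = 0.6 SD, active v placebo, stated power 82%. Assumed because not stated: two-sided alpha 0.05 (one-sided 0.05 also tried) and no loss. All figures are exact noncentral-t unless noted.

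**1. Reproducing 82%.** One-sample or paired t-test: noncentrality = d × √n = 0.6 × √25 = 3.00, df = 24, critical value 2.064. Power = **82.07%**. This matches the stated figure.

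**2. The comparison hypothesised, unadjusted.** Noncentrality = d × √(n/2) = 0.6 × √12.5 = 2.121.

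| Variant | Power |
|---|---|
| two-sided 5%, df 48 | 54.7% |
| two-sided 5%, pooled three-group error, df 72 | 55.3% |
| two-sided 5%, normal approximation | 56.4% |
| one-sided 5%, df 48 | 67.2% |

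The unstated alpha therefore does not explain the gap at either conventional choice.

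**3. What would give 82% unadjusted.** With 25 per group at two-sided 5%, d = 0.83 (noncentrality 0.83 × √12.5 = 2.93). At d = 0.6, 47 per group would be needed, or 3 × 47 = 141 in total. This is given for scale only.

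**4. Allowing for the planned ANCOVA.** With equal SDs at the two times, the residual SD is √(1 − r²) of the raw SD, and the SD of change is √(2(1 − r)) of it.
- If 0.6 is in raw SD units, effective d = 0.6/√(1 − r²).
- If 0.6 is in SD-of-change units, effective d = 0.6 × √(2(1 − r))/√(1 − r²) = 0.6/√((1 + r)/2).

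Two-sided 5%; the range runs from df 48 to the three-group error with one covariate (df 71):

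| r | raw SD: effective d | power | SD of change: effective d | power |
|---|---|---|---|---|
| 0.5 | 0.693 | 67-68% | 0.693 | 67-68% |
| 0.6 | 0.750 | 74% | 0.671 | 64-65% |
| 0.69 | 0.829 | 82% | 0.653 | 62% |
| 0.7 | 0.840 | 83% | 0.651 | 62% |
| 0.8 | 1.000 | 93-94% | 0.632 | 59-60% |

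On the raw scale power rises with r. On the change scale it falls, and 82% is reached only with r near zero (0.6/√0.525 = 0.828 at r = 0.05).

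**5. Illustration only.** The protocol gives no loss rate. At an assumed 10% or 20% loss (22.5 or 20 per group), the unadjusted 54.7% becomes 50% or 46%. Bonferroni for two comparisons (two-sided 2.5%) with no loss gives 43%. A multiplicity rule may properly sit in an analysis plan that is not shown.

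**The case against.** The best defence is that 55% is not the power of the planned analysis. Section 12.2 specifies ANCOVA, which gives more than the unadjusted comparison on either reading of the SD. On the raw scale, a correlation of 0.7 or above would meet or exceed 82%. This stands: 55% is the unadjusted figure, not what the trial delivers.

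A second defence uses the word 'or' in the hypothesis: success might mean that at least one active group beats placebo. If both supplements truly have a 0.6 SD effect, the chance of at least one significant result is about 83% at unadjusted one-sided 5% by normal approximation, and about 73% at two-sided 5%. Combined with ANCOVA at r = 0.5 on the raw scale, unadjusted two-sided 5% also comes to about 82%. So a raw-scale correlation of 0.69 is not the only route to the figure.

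A third point is that expecting no change on placebo is an ordinary planning assumption, which a correct two-sample calculation also makes. That stands too; the phrase is not itself an error.

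None of this validates 82%. Each route needs a correlation, an SD definition, a one-sided alpha or an any-success criterion with both supplements effective, and section 12.1 states none of them. Nor can the point be left to an analysis plan, because it concerns a figure printed in the protocol.

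**Conclusion.** The point holds in this form: 82% is not supported for the comparison with placebo to which section 12.1 attaches it. Unadjusted power for 0.6 SD is about 55% at two-sided 5%, some 27 points lower, and 67% at one-sided 5%. The unadjusted difference detectable with 82% power is about 0.83 SD at two-sided 5%. Power under the planned ANCOVA is higher but cannot be fixed from the protocol, because neither the correlation nor the SD is given. These results assume equal variances, approximate normality and no loss.

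A reader might infer two stronger things. One is that the sponsor did run a one-sample test. The match at 82.07% is suggestive, but the protocol names no test and other routes come near the same number. The other is that the trial will miss a true 0.6 SD effect almost half the time. That would follow only for an unadjusted analysis, which is not what section 12.2 plans.

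**What to change.** Keep 75 participants and rewrite section 12.1 for the between-group comparison. State alpha and sidedness, which SD the 0.6 refers to (raw PINP or change in PINP), whether the power is per comparison or for at least one of the two, and the number expected to be evaluable. Then do one of the following:

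- Preferably, give the power of the section 12.2 ANCOVA with an assumed baseline to 6-month PINP correlation and its source.
- Otherwise, give the unadjusted figures and label them so: with 25 evaluable per group and two-sided 5%, about 55% power for a 0.6 SD difference from placebo and 82% for 0.83 SD. Add that ANCOVA is expected to increase these by an amount not quantified.

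The expectation of no placebo change may stay as a planning assumption, provided the calculation carries the sampling error of the placebo mean. The cost is protocol wording and, unless a high raw-scale correlation can be sourced, a less favourable stated power. No participants, visits or analyses change.

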12.2 Proposed analyses

Analysis of the primary endpoint will be to evaluate changes in PINP in each treatment group between baseline and the study endpoint using by analysis of covariance (ANCOVA) to take account of baseline differences between groups.

Analysis of the secondary endpoints will similarly employ ANCOVA to evaluate differences between the treatment groups.

13. ADVERSE EVENTS

The Investigator, or a delegated researcher, is responsible for the detection and documentation of adverse events that may be related to participating in the study and that meet the criteria and definitions detailed below.

13.1 DEFINITIONS

An adverse event (AE) is an untoward medical occurrence in a study participant.

An adverse reaction (AR), in the context of this study, is any untoward and unintended response which is related to probiotics or dietary calcium supplements administered to that participant.

A serious adverse reaction (SAR) is any AR that:

- results in death of the clinical trial participant; is life threatening. A life-threatening AR refers to an event where the participant was at risk of death at the time of the event. It does not refer to an event which hypothetically might have caused death if it were more severe.
- requires in-patient hospitalisation[^] or prolongation of existing hospitalisation;
- results in persistent or significant disability or incapacity;
- consists of a congenital anomaly or birth defect;
- results in any other significant medical event not meeting the criteria above.

A suspected unexpected serious adverse reaction (SUSAR) is any AR that is classified as serious and is suspected to be caused by administration of the probiotics or dietary calcium supplements

[^]Any hospitalisation that was planned prior to randomisation will not meet seriousness criteria. Any hospitalisation that is planned post randomisation will meet the seriousness criteria unless it does not constitute an untoward medical occurrence (such as cosmetic elective surgery, social and/or convenience admission).

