8. STUDY ASSESSMENTS

8.1 Baseline visit

At the baseline visit, information will be collected on past medical history, current medications and medications taken during the previous 3 months. Diet will be assessed using a validated food frequency questionnaire (the Scottish Collaborative Group FFQ). Smoking and alcohol intake will be recorded.

The sites of Paget's disease will be recorded based on review of the medical records and the results of imaging. Analysis. The presence and severity of bone pain localised to sites affected by PDB will be recorded using a visual analogue scale with ratings from 0 (no pain) to 10 (the worst pain possible). Health related quality of life including bodily pain assessed by SF36 will also be recorded

A blood sample will be taken for routine biochemistry and haematology and sent to the local laboratory for analysis. An additional blood samples will be taken for analysis of specialised markers of bone metabolism, for genetic and epigenetic analysis and for transcriptome analysis. A stool and saliva sample will be obtained for analysis of the microbiome.

Following randomisation, participants will be given 3-month's supply of the intervention (probiotic, placebo or calcium and vitamin D supplement). Participants randomised to receive the probiotic or placebo will be advised that they should store the supplement in a refrigerator during the study. Participants randomised to the calcium and vitamin D supplements will be advised that the supplements should be stored at room temperature.

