13.3 RECORDING AEs AND ARs

All AEs, including post-operative complications, and mortality, will be recorded as part of the outcome measures in the study CRF. There is no requirement to complete an additional AE form.

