13.4 Detecting adverse events

Participants will be asked about the occurrence of AEs/SAEs at every visit during the study. Open-ended and non-leading verbal questioning of the participant will be used to enquire about AE/SAE occurrence. Participants will also be asked if they have been admitted to hospital, had any accidents, used any new medicines or changed concomitant medication regimens. If there is any doubt as to whether a clinical observation is an AE, the event will be recorded.

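### Section 13.1 defines adverse reactions only for the active products, so read literally no placebo event can be an AR or SAR, at odds with the protocol's own causality step

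*Protocol*

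**What the plan says.** The trial has three products. Section 8.1 states that after randomisation "participants will be given 3-month's supply of the intervention (probiotic, placebo or calcium and vitamin D supplement".

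Section 13.1 defines an AE without reference to arm: "An adverse event (AE) is an untoward medical occurrence in a study participant". It then narrows the AR to a response that "is any untoward and unintended response which is related to probiotics or dietary calcium supplements administered to that participant". A SAR is an AR that meets one of the listed seriousness criteria. A SUSAR "is any AR that is classified as serious and is suspected to be caused by administration of the probiotics or dietary calcium supplements".

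Collection is wider than these definitions. Section 13.3 states: "All AEs, including post-operative complications, and mortality, will be recorded as part of the outcome measures in the study CRF". Section 13.4 states: "Participants will be asked about the occurrence of AEs/SAEs at every visit during the study". The first of the two sections numbered 13.5 (causality) has the investigator rate any AE or SAE as unrelated, possibly related or probably related to the supplement. The second (severity) asks for a grade only for events thought possibly or probably related to the supplement.

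**The concern.** The AR definition lists two of the three products. A placebo participant receives neither, so on the literal wording nothing that happens to that participant is an AR, and hence nothing is a SAR or SUSAR. A count of ARs by arm made under this rule would show zero on placebo whatever happened there. Background complaints that investigators judge related would count only against the probiotic and the calcium/vitamin D arms.

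The definition also shapes what is collected. Seriousness criteria are attached to ARs alone, and severity is graded only for events related to the supplement. If sites take placebo to lie outside these terms, the information is never recorded for the control arm, and no later analysis can recover it.

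**Working it through.** The protocol states no figure on this point, so there is none to reproduce. The check is textual, followed by an illustration of size.

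**1. Who can have an AR.** Section 13.1 requires a relation to probiotics or dietary calcium supplements given to that participant. Section 4 describes the placebo as a capsule of maize starch, magnesium stearate and maltodextrin. A placebo participant is given neither named product, so the condition cannot be met. SAR inherits this, and SUSAR repeats the same two products ("is suspected to be caused by administration of the probiotics or dietary calcium supplements").

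**2. Does the causality step agree?** It applies to any AE or SAE and excludes no arm, but it rates against the supplement. The protocol uses that word in two ways:
- Section 8.1 tells participants on probiotic or placebo to keep the supplement refrigerated, so there the word includes the placebo capsule.
- Section 8.2 times the visit at "three months after commencing the supplement or placebo", and section 8.3 uses the same pairing, so there placebo is something other than the supplement.

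On the inclusive reading, a placebo event can be rated probably related in section 13.5 and still not be an AR in section 13.1. On the exclusive reading, placebo events have nothing to be rated against. The two sections do not fit together on either reading.

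**3. Severity.** Grading depends on relatedness to the supplement. On the exclusive reading, no placebo event is graded.

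**4. Seriousness.** SAE is used in section 13.4 and in the causality text but is not defined in section 13.1, where the seriousness criteria belong to ARs. Unrelated serious events therefore have no stated criteria in any arm. On placebo, under the literal AR rule, that covers every event.

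**5. SUSAR.** The term contains the word unexpected, but the definition has no such criterion. As written it is practically the same as SAR.

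**6. Illustration of size.** Inputs: 25 per arm (section 6.1); an assumed share *p* of participants with a background event labelled related, equal in all arms; placebo count set to zero by the literal rule; one active arm against placebo; two-sided Fisher exact test at 0.05. The protocol gives no value for *p* and plans no such test.

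For *x* of 25 against 0 of 25, the two-sided Fisher p-value is 2 × C(25,x) / C(50,x):
- x = 5: 2 × 53,130 / 2,118,760 = 0.0502
- x = 6: 2 × 177,100 / 15,890,700 = 0.0223

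Six or more events in the active arm are therefore needed for p<0.05, and the chance of a spurious result is P(X ≥ 6) for X ~ Binomial(25, p). The last column applies one definition to both arms and sums the same test over both binomial counts.

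| Assumed *p* | Placebo fixed at zero | One definition for both arms |
|---|---|---|
| 5% | 0.1% | 0.1% |
| 10% | 3.3% | 0.9% |
| 20% | 38% | 2.2% |
| 30% | 81% | 2.3% |

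**The case against.** The case for leaving the text alone has several parts.

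- **No AR comparison is planned.** Section 12.2 covers PINP and the secondary endpoints, and section 5 lists no safety endpoint. Safety tabulation is commonly left to the SAP. This stands. A reader might infer that the trial's adverse-reaction comparison is invalid, but the protocol contains no such comparison.
- **AEs are handled alike in every arm.** They are defined for any participant, asked about at every visit, all recorded, and all put to a causality rating. This stands too. An all-AE comparison is sound, and a count of related events taken from the causality ratings need not be zero on placebo. It does not reconcile the AR definition with those ratings, and it does not supply severity grades or seriousness criteria that the text ties to relatedness.
- **Section 8.1 already treats placebo as a supplement.** That is true of the storage instruction, but sections 8.2 and 8.3 separate the two. The usage is inconsistent, and sites could reasonably differ.
- **Applying the definition does not force unblinding.** A reader might infer that it does, because the capsules are identical. The documents do not support this: no blinding of the assessor is stated, and section 4 has the local PI or a delegate prescribe probiotic or placebo. That claim is not made here.
- **The size rests on assumption.** The documents give no rate of related events. At 10% the spurious rate is 3.3%, below the nominal 5%, and 5 against 0 just misses significance. The figures serve only as an illustration.
- **Vitamin D is part of one combined tablet**, so calling it a calcium supplement is natural shorthand. This is fair; naming it is tidying and carries no weight in the point.

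**Conclusion.** The point holds as a minor defect. It is a rule the protocol states, not a detail left to the SAP: section 13.1 leaves placebo out of AR, SAR and SUSAR, and this contradicts the causality step in section 13.5. Any AR or SAR count by arm made under the literal definition would be biased against the active arms. Placebo events may also go without a severity grade or a definition of seriousness.

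The primary and secondary endpoints, AE capture and all-AE counts are untouched. The bias matters only if ARs are tabulated by the literal definition and related background events are common. On the assumed rates it is small at 10% and large at 20% and above.

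**What to change.** - In section 13.1, define an AR as an untoward and unintended response related to any allocated study product: probiotic, placebo or calcium/vitamin D.
- Use *study product* in place of *supplement* throughout the SAR, SUSAR, causality and severity text.
- Apply the seriousness criteria to AEs in all arms, so that SAE is defined where it is already used.
- Make the SUSAR definition match its name by stating an unexpectedness criterion.
- Base any between-arm safety summary on all AEs as well as on related events.

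The cost is a wording amendment, with matching CRF labels where they repeat the old terms. Placebo participants will then show some adverse reactions, which is what a fair comparison needs.
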